4.1 SAMPLE SIZE

This is a single-arm, multi-center, prospective study. The sample size and study duration were determined to allow for an adequate safety profile of the investigational device. The study will be claimed successful if the incidence rates of severe hypoglycemia and diabetic ketoacidosis are considered acceptable compared to published rates.

In addition, a statistically powered sample size was determined for the two primary effectiveness endpoints. Since each of the primary effectiveness endpoints will be evaluated separately, the significance level will be adjusted so that the overall type I error can be maintained at one-sided 2.5%, and each endpoint will be tested at one-sided 1.25%.

A1C

The sample size estimation is based on the following assumptions:

- Mean difference between paired observations of A1C at the end of Phase 2 compared to baseline is -0.5%
- Standard deviation of the difference between paired observations of A1C at the end of Phase 2 participation compared to baseline is 0.8%
- Power of 90% and one-sided significance level of 1.25%

The estimates for the mean difference and standard deviation of the difference between the paired observations were obtained from previous Omnipod studies, where subjects experienced a mean change in A1C of 0.38% over 3 months (standard pump therapy only), from 8.1 to 7.7%, n=85 (data on file). Based on the above assumptions, 35 subjects are required to provide evaluable data.

Percentage of Time in Range 70-180 mg/dL

The sample size estimation is based on the following assumptions:

 Mean difference between paired observations of percentage of time in range 70-180 mg/dL during Phase 2 of hybrid closed-loop compared to Phase 1 is 10%

- Standard deviation of the difference between paired observations of percentage of time in range 70-180 mg/dL during Phase 2 of hybrid closed-loop compared to Phase 1 is 10%
- Power of 90% and one-sided significance level of 1.25%

The estimates for the mean difference and standard deviation of the difference between the paired observations were obtained from recent Omnipod Horizon study, G170143, where twelve (12) subjects aged 3.4-5.9 years experienced a mean change in percentage of time in range 70-180 mg/dL of 13.2 \pm 10.2%. Based on the above assumptions, 11 subjects are required to provide evaluable data.

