To gather adequate safety and effectiveness data on the performance of the Omnipod Horizon[™] System, the study plans to enroll up to 80 subjects to obtain a minimum of 60 evaluable subjects. Subjects will be enrolled across 6-12 clinical study sites. No single site should enroll more than 24 subjects.

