4.2 PRIMARY ANALYSIS

There are two primary effectiveness endpoints. The primary effectiveness endpoints will not be used to support labeling claims.

A1C

The end of Phase 2 (~13 weeks) A1C will be compared to baseline A1C as measured by the core laboratory by calculating the change from baseline in A1C at Visit 13 (~13 weeks) for each subject.

The change in A1C is calculated as the A1C at Visit 13 minus baseline A1C. The null hypothesis associated with this endpoint states that the mean change in A1C is greater than or equal to zero. Rejection of the null hypothesis indicates that the observed data support the alternative hypothesis that the mean change in A1C is less than zero (indicating improved glycemic control). The hypotheses associated with the first primary effectiveness endpoint are defined as:

H0: µ ≥ 0 H1: µ < 0

where μ is the mean of the per subject differences in A1C from baseline to Visit 13.

Percentage of Time in Range 70-180 mg/dL

The percentage of time in range (TIR) 70-180 mg/dL during Phase 2 of hybrid closed-loop will be compared to Phase 1 by calculating the change between the time in range percentages between Phase 2 and Phase 1 for each subject. The change is calculated as the percentage of time in range during Phase 2 minus the percentages of time in range

Statistical Analysis Plan

during Phase 1. The null hypothesis associated with this endpoint states that the mean change in percentage of time in range 70-180 mg/dL is less than or equal to zero. Rejection of the null hypothesis indicates that the observed data support the alternative hypothesis that the mean change in percentage of time in range 70-180 mg/dL is greater than zero. The hypotheses associated with the second primary effectiveness endpoint are defined as:

H0: µ ≤ 0 H1: µ > 0

where μ is the mean of the per subject differences in percentage of time in range 70-180 mg/dL during Phase 2 (hybrid closed-loop) compared to Phase 1 (standard therapy).

Both primary effectiveness endpoints will be tested independently of each other for statistical significance using a paired t-test at a one-sided significance level of 1.25%.

The modified Intention to Treat (mITT) analysis set will be the primary analysis set used to analyze the primary effectiveness endpoints. The results based on the Per Protocol (PP) analysis set will be considered supportive.

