If at least one of the primary effectiveness endpoints are found to be significant, the testing for secondary endpoints can commence. To maintain the family-wise error rate at one-sided 2.5% the testing will commence hierarchically, and Holm's correction will be applied as follows:

• A paired t-test will be applied to each of the secondary endpoints and the unadjusted p-values will be ordered from the smallest to largest.

- The hypothesis associated with the smallest unadjusted p-value will be tested for significance at a one-sided significance level of 2.5% / 2 = 1.25%.
- If the null hypothesis is rejected for the first hypothesis, the testing of the second hypothesis (with the higher unadjusted p-value) will commence, and the hypothesis will be tested for significance at a one-sided significance level of 2.5%. If the first null hypothesis is not rejected, the testing will stop.

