6.6 ANALYSIS OF SECONDARY EFFECTIVENESS ENDPOINTS WITHOUT PRESPECIFIED HYPOTHESES

There are no pre-specified hypotheses associated with the other secondary effectiveness endpoints. The mITT analysis set will be the primary analysis set used to analyze the secondary effectiveness endpoints. The results based on the PP analysis set will be considered supportive. Summary statistics will be presented by age cohort for all endpoints, stratified by time points of interest (e.g., day, night, overall). All statistical comparisons will be conducted at a two-sided significance level of 5%, with no adjustment for multiple testing. If the assumptions for parametric tests are grossly violated, a nonparametric method such as Wilcoxon signed rank test may be used. Since the results of endpoint analyses will not be used to support clinical claims, no adjustment for multiplicity will be performed.

As described in this document, results will be stratified by phase of the study (ST and HCL), and time of day (daytime: 6AM to <12AM and nighttime: 12AM to <6AM). Results for other subgroups (e.g., demographics, previous pump or CGM use, length of time in HCL) may be presented as appropriate. Data at Visit 13 will be used for any parameters that are measured at end of Phase 2. Data at Visit 19 will be used for any parameters that are measured at end of Phase 3.

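### Read as one rate over primaries and secondaries, the one-sided 2.5% family-wise rate in SAP 6.5 does not hold: it reaches about 3.7% if only one primary effect is real

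*SAP*

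**What the plan says.** SAP 4.1 divides the error rate over the two primaries, A1C and TIR, so that "the overall type I error can be maintained at one-sided 2.5%, and each endpoint will be tested at one-sided 1.25" percent. SAP 4.2 tests each with its own paired t-test at that level.

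SAP 6.5 then sets the gate to the two secondaries that carry hypotheses: "If at least one of the primary effectiveness endpoints are found to be significant, the testing for secondary endpoints can commence". The purpose follows directly: "To maintain the family-wise error rate at one-sided 2.5% the testing will commence hierarchically", with Holm's correction. The first Holm step reads "The hypothesis associated with the smallest unadjusted p-value will be tested for significance at a one-sided significance level of 2.5% / 2 = 1.25" percent. If it rejects, the other secondary is tested at 2.5%. These thresholds are the same whether one primary or both were significant.

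Protocol 13.4, which covers primary and secondary endpoints together, has the same gate. Its next sentence promises a one-sided family-wise rate of 2.5% and leaves the details to the SAP. Neither document lists the hypotheses that this 2.5% covers.

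Three statements bear on the consequence. SAP 2.4 rests study success on the rates of severe hypoglycemia and DKA. SAP 4.2 says "The primary effectiveness endpoints will not be used to support labeling claims". SAP 6.6, which deals only with secondaries without hypotheses, says "Since the results of endpoint analyses will not be used to support clinical claims, no adjustment for multiplicity will be performed".

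**The concern.** The primaries spend the full 2.5%. In a gatekeeping scheme, a significant primary can hand on only the alpha it was tested with, here 1.25%. SAP 6.5 hands the secondaries 2.5% even when the other primary has failed, which is twice what has been released.

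A reader who meets the gate, the hierarchy and the 2.5% in consecutive sentences will probably take 2.5% as the chance of any false claim among the four tests. At stake is whether that stated property is true. The labeling statement in SAP 4.2 names only the primaries, and the multiplicity waiver in SAP 6.6 covers only the secondaries without hypotheses. Neither reaches the two secondaries for which the sponsor chose to state an error rate.

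**Working it through.** **Inputs from the documents.** Each primary at one-sided 1.25% (SAP 4.1, 4.2); gate and Holm thresholds of 1.25%, then 2.5% (SAP 6.5); planned A1C change -0.5% with SD 0.8%, planned TIR change 10 points with SD 10 (SAP 4.1); at least 60 evaluable out of up to 80 enrolled (SAP 4.1). The primary analysis set is mITT (SAP 7.1.2), so n may lie between 60 and 80.

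**Assumed, because the documents do not give them.** SDs of the changes in the two secondaries, and all correlations. Ranges are shown.

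**1. The plan's own figure, one family at a time.**
- Primaries: 1.25% + 1.25% = 2.5%.
- Secondaries alone, both null and independent: 1 - 0.9875^2 = 2.48%. One null and the other surely rejected: 2.5%.

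So 2.5% is reproduced within each family.

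**2. All four tests together: where the rate holds.**
- Both primary nulls true: a false secondary claim needs a primary rejection first, and that is already a false claim. The rate is at most 1.25% + 1.25% = 2.5%.
- Both primary effects real: only the secondaries can err, and Holm holds them to 2.5%.
- Exactly one primary effect real: the ceiling is 1.25% (the null primary) + 2.5% (Holm) = 3.75%.

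**3. Case 1: TIR and one secondary improve; A1C and the other secondary do not.** TIR opens the gate (power above 99.9% at n = 60 on the planned effect). The improved secondary passes the first Holm step, so the null secondary is tested at 2.5%, while A1C is falsely rejected at 1.25%. If the two null tests are independent:

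1 - (1 - 0.0125)(1 - 0.025) = 1 - 0.9875 x 0.975 = 3.72%.

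By correlation of the two null test statistics (bivariate normal):

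| Correlation | -0.3 | 0 | +0.3 | +0.5 | +0.7 | +0.9 |
|---|---|---|---|---|---|---|
| Rate | 3.75% | 3.72% | 3.61% | 3.47% | 3.23% | 2.80% |

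By power p of the improved secondary at 1.25% (gate certain, tests independent), the rate is 0.0125 + 0.9875 x (0.0125 + 0.0125p): 3.60% at p = 0.9, 3.47% at 0.8, 3.10% at 0.5.

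**4. Simulation of case 1.** Paired t-tests, with the three CGM percentages forced to sum to 100%.
- Time <70 is the null secondary (>180 change -10, SD 10; <70 change 0, SD 2; correlation between them -0.3; A1C-TIR correlation 0 to 0.5): 3.68% to 3.72% at n = 60 and 3.68% to 3.76% at n = 80 (Monte Carlo standard error 0.03 points).
- Time >180 is the null secondary (SD 10; <70 change -2 with SD 3, or -1 with SD 2; correlation -0.3; n = 60): 3.5% to 3.7% if A1C is uncorrelated with >180, 3.0% to 3.3% if that correlation is +0.7.

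**5. Case 2: A1C improves and none of the three CGM measures does.** With SD 10 for the >180 change: 2.7% to 2.9% if the <70 SD is 2 to 3 (correlation 0 to -0.6), 2.9% to 3.1% if it is 5, and 3.0% to 3.7% if it is also 10 (correlation 0 to -0.9).

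**6. If only released alpha is passed on.** Case 1, independent: 1 - 0.9875 x 0.9875 = 2.48%. Case 2: 1.9% to 2.5%. In general, with one primary null, the rate is at most 1.25% + 1.25% = 2.5%.

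**The case against.** The strongest objection is about the reading. SAP 6.5 is a section on secondaries, and its Holm steps share alpha only among secondaries. SAP 4.1 already gives the primaries a self-contained 2.5%. On a reading of 2.5% per family, every stated rate is true. That reading is possible, and if it was meant the defect is one of wording. But Holm alone would control the secondary family. Presenting the gate and the hierarchy as the means of holding 2.5% points to a rate that spans both families, and Protocol 13.4 ties its promise to the same gate.

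The second objection is that 3.7% is a corner. It needs exactly one real primary effect, whereas the planned assumptions make both real. It needs A1C flat while TIR rises, which is unlikely if time above 180 falls by 10 points. It also needs high power for the improved secondary. All this stands as a limit on how often the excess would arise. With weak effects or a strong positive correlation it shrinks and can vanish. But a family-wise claim has to hold for every combination of true and false nulls, and this procedure does not meet that.

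The third objection, that little depends on the result, is largely right. Success rests on safety, no single secondary is tested above 2.5%, and nothing in the documents says that these two secondaries will support a claim.

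**Conclusion.** The concern holds on the natural, joint reading. The gated Holm procedure does not keep the rate over the four hypotheses at one-sided 2.5% when exactly one primary effect is real. The rate is then about 3.7% in case 1, with a ceiling of 3.75%. That figure assumes near-certain detection of TIR and of the improved secondary, and null tests that are roughly independent. Positive correlation or lower power brings it down to about 3% in the settings computed, and to 2.8% at a correlation of +0.9. Case 2 usually gives a smaller excess. The rate does hold when both primary nulls are true or both primary effects are real.

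On the separate-family reading there is no numerical error, only a failure to say which family is meant. Practical weight is moderate, but it should be fixed because a stated property of the analysis is not delivered.

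**What to change.** In SAP 6.5, pass on only the alpha of the primaries that were rejected:

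- both significant: Holm at a total of 2.5% (1.25%, then 2.5%);
- exactly one significant: Holm at a total of 1.25% (0.625%, then 1.25%);
- neither significant: stop.

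State that the 2.5% then covers all four hypotheses. If the sponsor instead intends a separate 2.5% for each family, one sentence saying so is enough, and the text should not present 2.5% as the rate over both.

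**Cost.** SAP wording only, with no added subjects. Thresholds change only when exactly one primary is significant. As TIR is almost certain to pass on the planned effect, that chance is close to one minus the A1C power (noncentral t, one-sided 1.25%, which also reproduces the SAP's 35 subjects for A1C):

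| A1C change (SD 0.8%) | n = 60 | n = 70 | n = 80 |
|---|---|---|---|
| 0.5% reduction, as planned | 0.63% | 0.19% | 0.06% |
| 0.38% reduction | 8.7% | 4.8% | 2.6% |

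The second row uses the SAP's cited data, in which "subjects experienced a mean change in A1C of 0.38% over 3 months (standard pump therapy only"); it was not obtained with this device. When the thresholds do halve, a secondary test with an assumed 90% power at 1.25% keeps about 85% at 0.625%: by normal approximation, 2.241 + 1.282 - 2.498 = 1.025, and the normal probability below 1.025 is 0.85.

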6.6 ANALYSIS OF SECONDARY EFFECTIVENESS ENDPOINTS WITHOUT PRESPECIFIED HYPOTHESES

There are no pre-specified hypotheses associated with the other secondary effectiveness endpoints. The mITT analysis set will be the primary analysis set used to analyze the secondary effectiveness endpoints. The results based on the PP analysis set will be considered supportive. Summary statistics will be presented by age cohort for all endpoints, stratified by time points of interest (e.g., day, night, overall). All statistical comparisons will be conducted at a two-sided significance level of 5%, with no adjustment for multiple testing. If the assumptions for parametric tests are grossly violated, a nonparametric method such as Wilcoxon signed rank test may be used. Since the results of endpoint analyses will not be used to support clinical claims, no adjustment for multiplicity will be performed.

As described in this document, results will be stratified by phase of the study (ST and HCL), and time of day (daytime: 6AM to <12AM and nighttime: 12AM to <6AM). Results for other subgroups (e.g., demographics, previous pump or CGM use, length of time in HCL) may be presented as appropriate. Data at Visit 13 will be used for any parameters that are measured at end of Phase 2. Data at Visit 19 will be used for any parameters that are measured at end of Phase 3.

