*Parents/guardians completing questionnaires must be the parent/guardian that provided consent for study participation, or subsequently signed a consent form. It is preferable that the parent/guardian completing a questionnaire at Screening (Visit 1) and Visit 2 is the same parent/guardian completing questionnaires at the End of Phase 2 (~13 weeks) or at the time of withdrawal from the study. No questionnaires will be completed during or at the conclusion of Phase 3.

Table 3: Schedule of Assessments for Phase 3

Assessment Schedule	Hybrid Closed-Loop (HCL)												UV	EW
	Phase 3													
Visit Number	14	15	16	17	18	19	20	21	22	23 or Study Exit	Extension Through Commercialization ^P			
Study Day/Visit Window	120 ± 5d	150 ± 5d	180 ± 5d	210 ± 5d	240 ± 5d	270 ± 5d	315 ± 5d	360 ± 5d	405 ± 5d	450 ± 5d	+ 45d ± 5d (or sooner if Study Exit)	-	-	
Telephone (T) or Office (O) Visit	T/O ^I	T/O ^I	T/O ^I	T/O ^I	T/O ^I	T/O ^I	T/O ^I	T/O ^I	T/O ^I	T/O ^I	T/O ^I	T/O ^I	O	
Laboratory Assessments														
A1C			X			X		X		X			X	
Clinical Assessments														
Informed Consent						X ⁿ				X ⁿ				
Concomitant Medications	X	X	X	X	X	X	X	X	X	X	X	X	X	
Height										X			X	
Weight										X			X	
Adverse Events	X	X	X	X	X	X	X	X	X	X	X	X	X	
Study Devices														
Return Horizon System										X	X		X	
Complaints/Device Deficiencies	X	X	X	X	X	X	X	X	X	X	X	X	X	
Device Uploads (BG/Ketone Meter)	X	X	X	X	X	X	X	X	X	X	X		X	

Data Review^m	X	X	X	X	X	X	X	X	X	X	X	X	X	X
--------------------------------	---	---	---	---	---	---	---	---	---	---	---	---	---	---

^lDevice uploads from the BG and Ketone meter are not required at any visit conducted via telephone.

^mData review for Horizon Automated Mode occur at all visits. Data review for BG/Ketone Meters to occur during onsite visits only.

ⁿSubjects extending their participation into the extension phase are to be consented for both the first 6-month and the second 6-month extension, as well as the extension through commercial availability. Consent for each interval must occur on or any time before commencing that study interval (e.g. consent for first 6-months of Phase 3 must occur on or before Visit 13, consent for second 6-months of Phase 3 must occur on or before Visit 19, consent for visits beyond Visit 23 until commercial availability must occur on or before Visit 23).

^oDevices will be returned to the site at the end of the subject’s participation if the subject is not participating in the extension phase.

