6.3.1 Secondary Endpoints

The secondary objective will be evaluated using the following per subject endpoints *with* prespecified hypotheses:

- Glucose metrics from system CGM during the hybrid closed-loop phase for Phase 2 will be compared to Phase 1 overall:
 - % of time > 180 mg/dL
 - % of time < 70 mg/dL

Additional per subject secondary endpoints *without* prespecified hypotheses used to evaluate the secondary objective include:

- A1C:
 - A1C at the end of Phase 2 (Visit 13), at 6 months (Visit 16), and at the end of Phase 3 (Visit 23; approximately 15 months)

- Change from baseline in A1C at the end of Phase 2 (Visit 13), at 6 months (Visit 16), and at the end of Phase 3 (Visit 23; approximately 15 months)
- Proportion of subjects demonstrating an improvement from baseline in A1C at the end of Phase 2 (Visit 13), at 6 months (Visit 16), and at the end of Phase 3 (Visit 23; approximately 15 months)
- Glucose metrics from system CGM during the hybrid closed-loop phase during Phase 2, and separately during Phase 3 will be compared to Phase 1 during the day, overnight, and overall:
 - Mean glucose
 - % of time in range 70-180 mg/dL
 - % of time in range 70-140 mg/dL
 - % of time > 180 mg/dL
 - % of time \geq 250 mg/dL
 - % of time \geq 300 mg/dL
 - % of time < 70 mg/dL
 - % of time < 54 mg/dL
 - Standard deviation
 - Coefficient of variation
- Percentage of time in hybrid closed-loop as proportion of overall device usage time during Phase 2, and separately during Phase 3
- Glucose management indicator (GMI) based on overall mean glucose during Phase 2 and, separately during Phase 3 will be compared to Phase 1
- Insulin requirements during Phase 2 and, separately during Phase 3 will be compared to Phase 1:
 - Total daily insulin (TDI) (units, units/kg)
 - Total daily basal insulin (units, units/kg)
 - Total daily bolus insulin (units, units/kg)
- Change from baseline in BMI (kg/m²) at end of Phase 2, and at the end of Phase 3

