Visit 15 will be conducted either over the telephone or in person at the clinical study site on Study Day 150 ± 5 days. This visit will include:

- Review of concomitant medications
- Assessment of AEs since last visit
- Complaints/device deficiencies such as occlusion alarms and system hazard alarms since last visit
- Device uploads for BG and ketone meter (if visit is conducted at the clinical site)
- Data review of Automated Mode use by clinician

10.3 Visit 16

Visit 16 will be conducted either over the telephone or in person at the clinical study site on Study Day 180 ± 5 days. This visit will include:

- A1C (blood sample sent to NGSP laboratory)
- Review of concomitant medications
- Assessment of AEs since last visit
- Complaints/device deficiencies such as occlusion alarms and system hazard alarms since last visit

- Device uploads for BG and ketone meter (if visit is conducted at the clinical site)
- Data review of Automated Mode use by clinician

10.4 Visits 17 and 18

Visits 17 and 18 will be conducted either over the telephone or in person at the clinical study site on Study Day 210 \pm 5 days and Study Day 240 \pm 5 days, respectively. These visits will include:

- Review of concomitant medications
- Assessment of AEs since last visit
- Complaints/device deficiencies such as occlusion alarms and system hazard alarms since last visit
- Device uploads for BG and ketone meter (if visit is conducted at the clinical site)
- Data review of Automated Mode use by clinician

10.5 Visit 19

Visit 19 will be conducted either over the telephone or in person at the clinical study site on Study Day 270 \pm 5 days. This visit will include:

- A1C (blood sample sent to NGSP laboratory)
- Informed Consent (consent for second 6-month interval of Phase 3 may occur on or any time before this visit)
- Review of concomitant medications
- Assessment of AEs since last visit
- Complaints/device deficiencies such as occlusion alarms and system hazard alarms since last visit
- Device uploads for BG and ketone meter (if visit is conducted at the clinical site)
- Data review of Automated Mode use by clinician

10.6 Visit 20

Visit 20 will be conducted either over the telephone or in person at the clinical study site on Study Day 315 \pm 5 days. This visit will include:

- Review of concomitant medications
- Assessment of AEs since previous visit
- Complaints/device deficiencies such as occlusion alarms and system hazard alarms since last visit

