2.3 STUDY SCHEDULE

The study will consist of a 14-day outpatient standard therapy (ST) outpatient phase (Phase 1), a 13-week outpatient hybrid closed-loop (HCL) phase (Phase 2), and a 6-month hybrid closed-loop extension phase (Phase 3). The sponsor intends to submit results from Phase 2 for marketing clearance after data collection for Phase 2 is complete.

The Horizon[™] System has two modes. In Manual Mode, the system will function equivalently to the Omnipod DASH System. This includes delivering insulin at programmed basal rates and bolus amounts with the option to set temporary basal profiles. In Automated Mode, the system will support the use of multiple target glucose values. The

Statistical Analysis Plan

programmed basal rates, glucose targets and bolus calculator settings will inform the MPC (model predictive control) algorithm for insulin dosing parameters.

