3.3 SECONDARY OBJECTIVE AND ENDPOINTS

The secondary objective is to evaluate additional glycemic measures of effectiveness of the Omnipod Horizon[™] Automated Glucose Control System. The secondary objective will be evaluated based on the following per subject endpoints *with* prespecified hypotheses:

- Glucose metrics from system CGM during the hybrid closed-loop phase for Phase 2 will be compared to Phase 1 overall:
 - Percentage of time in range > 180 mg/dL
 - Percentage of time in range < 70 mg/dL

Additional per subject endpoints *without* prespecified hypotheses used to evaluate the secondary objective include:

- A1C:
 - A1C at the end of Phase 2 (Visit 13), 6 months (Visit 16) and the end of Phase 3 (Visit 19)
 - Change from baseline in A1C at the end of Phase 2 (Visit 13), 6 months (Visit 16) and the end of Phase 3 (Visit 19)
 - Proportion of subjects demonstrating an improvement from baseline in A1C at the end of Phase 2 (Visit 13), 6 months (Visit 16) and the end of Phase 3 (Visit 19)
- Glucose metrics from system CGM during the hybrid closed-loop phase for Phase 2 and Phase 3 will be compared to Phase 1 during the day, overnight, and overall:
 - Mean glucose
 - Percentage of time in range 70-180 mg/dL
 - Percentage of time in range 70-140 mg/dL
 - Percentage of time in range > 180 mg/dL
 - Percentage of time in range ≥ 250 mg/dL
 - Percentage of time in range \geq 300 mg/dL
 - Percentage of time in range < 70 mg/dL
 - Percentage of time in range < 54 mg/dL
 - Standard deviation
 - Coefficient of variation
- Percentage of time in hybrid closed-loop as proportion of overall device usage time during Phase 2 and Phase 3
- Glucose management indicator (GMI) based on overall mean glucose during Phase 2 and Phase 3 will be compared to Phase 1
- Insulin requirements during Phase 2 and Phase 3 will be compared to Phase 1:
 - Total daily insulin (TDI) (units, units/kg)
 - Total daily basal insulin (units, units/kg)
 - Total daily bolus insulin (units, units/kg)
- Change from baseline in BMI (kg/m²) at end of Phase 2 and Phase 3

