7.6 EXPLORATORY ANALYSES

The following exploratory analyses will be considered. The analyses may be used for internal research purposes and/or scientific presentations and/or manuscripts and may not all be provided in a regulatory submission:

- Number of hypoglycemic and hyperglycemic events as measured by the system CGM during the hybrid closed-loop phase will be compared to Phase 1
- Glucose metrics from the system CGM during Phase 2 stratified by device mode
- Change from baseline in A1C and BMI at the last follow-up visit, given at least 8weeks of participation in Phase 2
- Change from baseline in A1C at end of Phase 2, stratified by baseline A1C (e.g. A1C ≥7.5%, ≥9.0%)
- Proportion of subjects with A1C <7.0% at baseline and end of Phase 2; similar analyses using A1C cutoffs of <7.5%, <8.0% and <9.0%
- Proportion of subjects with change from baseline in A1C at end of Phase 2 of >0.5% and >1.0%

- Proportion of subjects who either had an improvement from baseline of >1.0% in A1C or A1C <7.0% at end of Phase 2
- Percentage of time the CGM was used during Phase 2
- Number of meal and correction boluses
- Compare glycemic outcomes (e.g., TIR <70 mg/dL, TIR >180 mg/dL) by bolus frequency per day
- Compare glycemic outcomes (e.g., TIR <70 mg/dL, TIR >180 mg/dL) by use of CGM informed bolus calculator (i.e., days with CGM informed bolus calculator used at least once and days without CGM informed bolus calculator use)
- Glycemic outcomes and other measures based on evaluable subjects (i.e., those subjects with at least 8 weeks of data during Phase 2)

The results of exploratory analyses will be presented using summary statistics. Data at Visit 13 will be used for any parameters that are measured at end of Phase 2 (data at Visit 19 will be used for any parameters that are measured at end of Phase 3). Any statistical testing will be performed at a two-sided significance level of 5% with no adjustment for multiple testing. If the observed data are found not to follow a normal distribution, non-parametric methods may be employed (such as Wilcoxon rank sum test as appropriate).

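### The SAP takes end-of-Phase-3 values from Visit 19 (day 270) while the protocol's end-of-Phase-3 A1C is at Visit 23 (day 450); at Visit 19 the SAP's BMI endpoint has no scheduled height or weight for subjects who continue

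*SAP*

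**What the plan says.** **SAP.** Section 2.3 describes "a 6-month hybrid closed-loop extension phase (Phase 3"). Section 3.3 lists the A1C time points after Phase 2 as "6 months (Visit 16) and the end of Phase 3 (Visit 19"), and also lists "Change from baseline in BMI (kg/m²) at end of Phase 2 and Phase 3". Section 6.6 then gives a general rule for the secondary endpoints without hypotheses: "Data at Visit 19 will be used for any parameters that are measured at end of Phase 3". Section 7.6 repeats it for the exploratory analyses: "data at Visit 19 will be used for any parameters that are measured at end of Phase 3".

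**Protocol.** The Protocol Summary and sections 6.3.1 and 13.1.4 each put the last of their A1C time points "at the end of Phase 3 (Visit 23; approximately 15 months"). The BMI bullet in the same lists refers to the end of Phase 3 without naming a visit. Section 10.5 and the footnotes to Table 3 make Visit 19 an intermediate visit with its own consent step: "consent for second 6-months of Phase 3 must occur on or before Visit 19".

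**Precedence.** SAP 1 and Protocol 13.10 both say that the SAP governs where the two differ.

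**The concern.** The two documents attach the same label, end of Phase 3, to visits about six months apart, and the precedence rule resolves the conflict in favour of the earlier visit. An analyst who follows the rules would report a 9-month A1C under that label, although a 15-month A1C is collected and is the protocol's own end-of-Phase-3 value.

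For BMI the problem is more than a label. The SAP asks for a change from baseline at a visit where the protocol does not schedule height or weight. Any scheduled measurements near Visit 19 would come from children leaving the study at about that time, who are a selected group. The Phase 3 results are to be submitted separately (Protocol Summary, study duration), so the mismatch would carry into a regulatory document.

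**Working it through.** **Inputs**

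- Visit 13, which starts Phase 3: day 94 ± 3 (Protocol 9.9 and 10).
- Visit 19: day 270 ± 5 (Protocol 10.5).
- Visit 23: day 450 ± 5 (Protocol 10.9).
- Height, weight and A1C marks: Protocol Table 3, checked against the visit lists in 10.1 to 10.10 and 10.12.
- Conversion: 30.44 days per month.

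**Step 1: each document's own figures.** Elapsed months = days / 30.44.

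| Quantity | Calculation | Result | Stated figure |
|---|---|---|---|
| Protocol end of Phase 3, from closed-loop start | 450 / 30.44 | 14.8 months | about 15 months (6.3.1) |
| Protocol length of Phase 3 to Visit 23 | (450 − 94) / 30.44 | 11.7 months | about 12 months (section 10) |
| SAP end of Phase 3, from closed-loop start | 270 / 30.44 | 8.9 months | none given |
| SAP length of Phase 3 to Visit 19 | (270 − 94) / 30.44 | 5.8 months | 6 months (2.3) |

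Each document agrees with its own timeline. The difference is therefore two definitions of Phase 3, not a mistyped visit number.

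**Step 2: the gap.** 450 − 270 = 180 days by schedule. With the windows, the smallest gap is 445 − 275 = 170 days and the largest is 455 − 265 = 190 days.

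**Step 3: what is scheduled at each candidate visit.**

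| Measure | Visit 19 | Visit 23 or study exit | Early withdrawal | Other Phase 3 visits |
|---|---|---|---|---|
| A1C | yes | yes | yes | Visits 16 and 21 |
| Height | no | yes | yes | none |
| Weight | no | yes | yes | none |

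The visit lists agree with the table: 10.5 (Visit 19) has A1C but neither height nor weight, 10.9 (Visit 23) has all three, and 10.12 (early withdrawal) has all three. The commercialization visits in 10.10 list none of them.

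**Step 4: consequence for each endpoint.** A1C can be computed under the SAP rule, but at 8.9 rather than 14.8 months. BMI needs both height and weight at follow-up. For a subject who continues past Visit 19, neither is scheduled there, so the end-of-Phase-3 BMI change cannot be produced from scheduled data.

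**The case against.** The strongest reply is that the SAP has other routes to the later data. Section 7.1 says that Phase 3 endpoints will be summarized from all available data, and 7.6 includes an analysis of A1C and BMI change at the last follow-up visit for subjects with at least 8 weeks in Phase 2. Read plainly, the latter could use a Visit 23 height, weight and A1C. Both soften the point, but neither replaces the visit rule. The 7.1 sentence concerns analysis sets; it does not override a specific visit, and it cannot supply a measurement that Visit 19 does not schedule. The 7.6 analysis is exploratory, is only to be considered, and could be read as limited to Phase 2.

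Two further objections stand as limits. First, the protocol ties Visit 23 explicitly only to A1C; for BMI, Visit 23 is inferred from the assessment schedule. Second, the schedule is unclear about study exit. Table 3 pairs Visit 23 with study exit, yet the commercialization visits, which end with a study exit visit, carry no height, weight or A1C marks.

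It is also fair to say that the practical loss is small. Visit 19 A1C is itself listed in Protocol 6.2.1, and the Visit 23 measurements are scheduled whatever the SAP says. A reader might infer that the 15-month A1C, or the protocol's Phase 3 rates of severe hypoglycemia and DKA, have been dropped because the SAP does not name them. The documents do not support that. The precedence rule applies to discrepancies, and silence is not one. The protocol still lists both (6.1.1, 6.2.1), and SAP 5.4 tabulates adverse events by study phase.

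**Conclusion.** The conflict is real and should be corrected before the Phase 3 analysis. As the documents stand, the governing text labels a value at 8.9 months as end of Phase 3 where the protocol's A1C value is at 14.8 months, and it defines a BMI endpoint with no scheduled input for continuing subjects.

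The reach is limited to descriptive Phase 3 results. A reader might infer a threat to the trial's main conclusions, but the documents rule that out. Phase 3 endpoints carry no hypotheses (Protocol 13.4), study success rests on Phase 2 event rates (SAP 2.4), and SAP 6.6 says that these secondary results will not support clinical claims. Nor is BMI impossible for everyone: a subject leaving at about Visit 19 could have height and weight under the study-exit or early-withdrawal column.

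The conclusion rests on the scheduled days and on reading Table 3 together with the visit lists, which agree at Visits 19 and 23. The documents do not say why the two definitions differ, and the conclusion does not depend on the reason.

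**What to change.** - **SAP 3.3, 6.6 and 7.6:** replace Visit 19 with Visit 23 for end-of-Phase-3 parameters. Keep the Visit 19 A1C, labelled as a 9-month time point.
- **BMI:** state that the end-of-Phase-3 value uses Visit 23, and report it with the number of subjects who have measured height and weight.
- **SAP 2.3:** reconcile the 6-month length of Phase 3 with the protocol. The protocol needs its own reconciliation, since section 10 gives about 12 months while the Protocol Summary and 5.2 run Phase 3 until commercial availability.

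The cost is amendment wording and revised Phase 3 tables, with no added visits or assessments. The downside is that Protocol 10.9 allows Visit 23 by telephone, so some heights and weights may be missing and the BMI summary may rest on fewer subjects than the A1C summary.
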